2.1.4 Safety endpoints

The safety analysis will be based on the reported adverse events and other safety information, such as clinical laboratory data, vital signs and physical examination.

Observation period

The observation period will be divided into 2 non mutually exclusive periods: the on-study period and the recurrence period.

The on-study observation period is defined as the time from informed consent until the end of the study (defined as last protocol planned visit).

The recurrence period is from the start of the recurrence episode, defined as recurrent thrombocytopenia requiring initiation of daily PE, until the last recurrence follow-up visit of that episode. In case of treatment with the IMP, the recurrence period is divided into 2 epochs:

- the **treatment epoch** is defined as the time from the first administration of the IMP to the last administration of the IMP.
- the **residual treatment** epoch is defined as the time from the last administration of the IMP to the last administration of the IMP + 30 days.

The treatment-emergent adverse event (TEAE) period will include both treatment and residual treatment epochs.

In case treatment with the IMP is not initiated during the recurrence episode, there is no subdivision of the recurrence period into the treatment epoch and the residual treatment epoch. The adverse event occurring during that period are not identified as treatment-emergent adverse events.

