2.4.5 Analyses of safety data

The summary of safety results will be presented by treatment group. For the ITO population, the treatment groups are:

- Caplacizumab total: Subjects who received caplacizumab during the ALX0681-C301 study (during the double blind or the open-label periods).
- Not treated: Subjects who never received Caplacizumab during the ALX0681-C301 trial

For the recurrence population, adverse events will be presented for:

- Treated with IMP: patients treated with caplacizumab in the ALX0681-C302 study
- Not Treated with IMP: patients not treated with caplacizumab in the ALX0681-C302 study during the trial

General common rules

All safety analyses will be performed on the ITO and recurrence populations as defined in [Section 2.3.2](#), unless otherwise specified, using the following common rules:

- For analysis related to the Q6M FU visits, the baseline value is defined as screening/baseline value visit. For analysis related to the recurrence period, the baseline value is defined as the recurrence visit value and will be calculated for each recurrence period separately
- For assessments with multiple parameters per participant (such as laboratory assessments), baseline will be determined per parameter individually. It is recognized that baseline assessments may thus come from more than one assessment and not just from the “baseline visit” assessment.
- For quantitative safety parameters based on central laboratory/reading measurements, descriptive statistics will be used to summarize results and change from baseline values by visit.
- The analysis of the safety variables will be essentially descriptive, and no systematic testing is planned.

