2.4.5.1 Analyses of adverse events

Generalities

The primary focus of adverse event reporting will be on treatment-emergent adverse events. Pretreatment and posttreatment adverse events will be described separately.

If an adverse event date/time of onset (occurrence, worsening, or becoming serious) is incomplete, an imputation algorithm will be used to classify the adverse event as pretreatment,

treatment-emergent, or posttreatment. The algorithm for imputing date/time of onset will be conservative and will classify an adverse event as treatment emergent unless there is definitive information to determine it is pretreatment or posttreatment. Details on classification of adverse events with missing or partial onset dates are provided in [Section 2.5.3](#).

Adverse events (AEs) will be placed into analysis periods according to their start date (time). The AE will only be presented in the analysis period during which it started, ie, period start date (time) \leq AE start date (time) \leq period stop date (time). There will be no imputation of other missing date (time) fields, nor of the missing parts of other partially known date (time) fields. When needed (e.g., an incomplete date (time) leads to a double phase allocation), the following rules will be applied: adverse events will be allocated on all analysis levels (ie, for analysis periods and subperiods, see [Section 2.5.4](#)) according to their start date (time). In case the adverse event (AE) start date(time) is incomplete, the allocation will be done according to the available parts of the AE start date(time) and taking into account the AE end date(time) (ie, the AE start date(time) cannot be later than the AE end date(time)):

- When, due to missing date (part) an allocation needs to be made to an analysis period, the AE will be allocated to the treatment phase and not off-treatment phase (worst-case allocation).
- When an allocation needs to be made to a specific recurrence period, the AE will be allocated to the first recurrence period.
- When an allocation needs to be made within a recurrence period, the event will be allocated to the daily PE subperiod.

Tables on the recurrence population will include only adverse events that occurred during the recurrence period, treatment-emergent (for patients who received the IMP) and non-treatment emergent (for patients who did not received the IMP).

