When cross-tabulating AE PTs versus an AE attribute (e.g., severity), the worst-case is always applied within each analysis period. This means that when a participant has the same AE PT twice in the same analysis period, then the participant is reported only once: with the worst severity. If this happens in two different analysis periods, the participant is reported twice: once in each analysis period.

AE onset day and AE duration are defined as follows:

- AE onset day
 - AE start date – reference date + 1 day (when the AE start date is completely known)
 - Missing (when the AE start date is incomplete or unknown).
 - Two different onset days will be calculated: one with the reference date being the screening/baseline visit; and the other, for adverse events occurring during the recurrence period, with reference date being the recurrence visit.
- AE duration
 - AE stop date – AE start date + 1 day (when both dates are completely known)

- Trial termination date – AE start date + 1 day (when the AE start date is fully known but the AE is not resolved at the end of the trial): in this case the duration will be presented as “>x days” in the listing rather than “x days”
- Missing (when the AE start date is incomplete or unknown, or when the AE has resolved but with an incomplete or unknown end date).

These derived parameters will only be presented in the listings. Note that the start and stop times of the AE are not used.

AE incidence tables will present by SOC and PT, sorted by decreasing frequency of SOC and PTs within SOCs, the number (n) and percentage (%) of participants experiencing an adverse event. The denominator for computation of percentages is the population within each treatment group.

The following analysis periods will be considered for all TEAEs tables on the recurrence population:

- Treatment daily PE period
- Treatment post-daily PE period
- Overall treatment period
- Follow-up period
- Overall recurrence period

The following analysis periods will be considered for AE occurring in the recurrence periods for patients not treated with the IMP:

- Daily PE period
- Post Daily PE period
- Overall recurrence period

The following analysis period will be considered for the adverse events observed during the study for the ITO population:

- Overall study period

Analysis of all adverse events

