The following adverse event summaries will be generated by analysis period for the patients not treated in the recurrence population and for the ITO population.

- Overview of adverse events, summarizing number (%) of participants, the number of events, and the incidence per 100 person months, which will be calculated as: $100 \times (\text{Number of participants with AE}) / (\text{Total number of months observed within analysis period, summed for all participants})$ with any
 - Participants with at least one AE
 - Participants with at least one serious AE

- Participants with at least one AE leading to death
- Participants with at least one PE-related AE (only for the recurrence population)
- Participants with at least one serious PE-related AE (only for the recurrence population)
- Participants with at least one bleeding event, i.e. an event documented as event indicating an increased bleeding tendency
- Participants with at least one bleeding event, based on the Standardized MedDRA Query (SMQ) “Haemorrhage” with exclusion of the PT “TTP”
- Participants with at least one thromboembolic event, based on the SMQ “Embolic and thrombotic events” (arterial, venous, and vessel type unspecified and mixed arterial and venous) with exclusion of the PT “TTP”
- All AE by primary SOC and PT, showing the number (%) of participants with at least 1 AE. The number of events and the number and percentage of participants having an event will be presented.
- AEs will be summarized by SOC, PT and severity. This will be done for each analysis period. The number and percentage of participants having an event will be presented for the worst severity reported for each event.

Analysis of all treatment-emergent adverse events

The following treatment-emergent adverse event summaries will be generated by analysis period for the recurrence population.

- Overview of treatment-emergent adverse events, summarizing number (%) of participants, the number of events, and the incidence per 100 person months, which will be calculated as: $100 \times (\text{Number of participants with AE}) / (\text{Total number of months observed within analysis period, summed for all participants})$ with any
 - Participants with at least one TEAE
 - Participants with at least one serious TEAE
 - Participants with at least one TEAE leading to death
 - Participants with at least one TEAE for which the study drug was interrupted
 - Participants with at least one TEAE for which the study drug was withdrawn

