 - Participants with at least one TEAE that was considered treatment-related by the investigator
 - Participants with at least one serious TEAE that was considered treatment-related by the investigator
 - Participants with at least one PE-related TEAE
 - Participants with at least one serious PE-related TEAE
 - Participants with at least one bleeding event, i.e. an event documented as event indicating an increased bleeding tendency

- Participants with at least one bleeding event, based on the Standardized MedDRA Query (SMQ) “Haemorrhage” with exclusion of the PT “TTP”
- Participants with at least one thromboembolic event, based on the SMQ “Embolic and thrombotic events” (arterial, venous, and vessel type unspecified and mixed arterial and venous) with exclusion of the PT “TTP”
- Participants with at least one hypersensitivity reaction, based on the SMQs “Hypersensitivity” (Narrow), “Anaphylactic reaction” (Narrow) and “Angioedema” (Narrow)
- Participants with at least one hypersensitivity reaction, based on the SMQs “Hypersensitivity” (Narrow), “Anaphylactic reaction” (Narrow) and “Angioedema” (Narrow), considered treatment-related by the investigator.
- All TEAE by primary SOC and PT, showing the number (%) of participants with at least 1 TEAE. The number of events and the number and percentage of participants having an event will be presented.
- TEAEs will be summarized by SOC, PT and severity. This will be done for each analysis period. The number and percentage of participants having an event will be presented for the worst severity reported for each event.
- TEAEs considered treatment-related by the investigator will be summarized by SOC and PT. This will be done for each analysis period. The number of events and the number and percentage of participants having an event will be presented.

Analysis of all (treatment emergent) serious adverse event(s)

- Serious (TE)AEs and non-serious (TE)AEs will be summarized by SOC and PT. This will be done for each analysis period. The number of events and the number and percentage of participants having an event will be presented.
- Serious (TE)AEs will be summarized by SOC, PT and severity. This will be done for each analysis period. The number and percentage of participants having an event will be presented for the worst severity reported for each event.

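### Adverse events are treatment-emergent up to 30 days after the last dose, but the tables for them stop at the visit about 7 days after treatment

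*SAP*

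**What the plan says.** SAP 2.1.4 starts the recurrence period at the recurrence and runs it "until the last recurrence follow-up visit of that episode". It continues: "In case of treatment with the IMP, the recurrence period is divided into 2 epochs". The first is the treatment epoch, from first to last dose. The second, or residual, "epoch is defined as the time from the last administration of the IMP to the last administration of the IMP + 30 days". The TEAE period is both epochs together, and SAP 2.1.4.1 and 2.1.4.2 use it to define TEAEs and on-treatment deaths.

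The reporting rules are in SAP 2.4.5.1:

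- On population: "The following treatment-emergent adverse event summaries will be generated by analysis period for the recurrence population".
- On content: "Tables on the recurrence population will include only adverse events that occurred during the recurrence period".
- On periods: "The following analysis periods will be considered for all TEAEs tables on the recurrence population". Five follow: daily PE on treatment, post-daily PE on treatment, overall treatment, follow-up, and overall recurrence.
- Each event is placed only in the period in which it started.

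SAP 2.5.4, Table 1 ends the follow-up period of a treated episode on the date of the recurrence follow-up visit. SAP Appendix A, Table 5 and Protocol Table 2 schedule that visit 7 (±1) days after the end of caplacizumab.

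**The concern.** A period that closes about a week after the last dose cannot contain an epoch that closes 30 days after it. The tables are built on the shorter limit, so the later part of the defined TEAE window has no table to go into.

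This bears on a study objective. SAP 1.2 lists the safety of repeated use of caplacizumab, and SAP 2.4.5.1 makes TEAEs the main focus of adverse event reporting. A late event still appears in the whole-study tables of the intention-to-observe (ITO) population. There, SAP 2.4.5 groups subjects by whether they received caplacizumab in ALX0681-C301, so the event is not tied to retreatment in ALX0681-C302. The ITO overview also has no row for events the investigator considered treatment-related; that row exists only in the TEAE overview.

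Two programmers, one following the definition and one following the table periods, can produce different TEAE counts from the same data.

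**Working it through.** The plan gives no figure for the overlap to reproduce, so the check is calendar arithmetic.

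**Inputs**

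- End of the TEAE window: last dose + 30 days (SAP 2.1.4).
- End of the last TEAE table period: recurrence follow-up visit (SAP 2.5.4, Table 1).
- Day of that visit after end of treatment: 7, allowed range 6 to 8 (SAP Appendix A, Table 5).
- Assumption: the end of the treatment period in Table 1, which is not defined there, is the date of the last dose.

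**Uncovered days** = 30 − visit day

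| Visit day | Covered | Uncovered | Days | Share of 30 |
|---|---|---|---|---|
| 6 | 1–6 | 7–30 | 24 | 80% |
| 7 | 1–7 | 8–30 | 23 | 77% |
| 8 | 1–8 | 9–30 | 22 | 73% |

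**Share of the whole TEAE window.** This needs a length for the daily PE period, which the plan does not give for recurrences. I assume 5.9 days, the mean for the initial daily PE period in the caplacizumab arm of the Phase II study (Protocol 1.2.4).

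- No extension: 5.9 + 30 + 30 = 65.9 days; 23/65.9 = 34.9% (22/65.9 = 33.4%; 24/65.9 = 36.4%).
- Full 28-day extension: 5.9 + 30 + 28 + 30 = 93.9 days; 23/93.9 = 24.5% (22/93.9 = 23.4%; 24/93.9 = 25.6%).
- The PE assumption matters little. With 3 PE days the shares are 23/63 = 36.5% and 23/91 = 25.3%; with 10 PE days they are 23/70 = 32.9% and 23/98 = 23.5%.

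**When the gap shrinks.** Protocol 3.2.4.2 keeps subjects who stop drug on the original visit schedule. If drug stops k days early and the visit does not move, the gap is 30 − (7 + k) = 23 − k days, and it is nil from k = 23. It also ends when a new recurrence opens a new episode.

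**Consequences elsewhere in the SAP**

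- A subject with a fatal event that starts, and ends in death, on day 15 after the last dose is an on-treatment death under SAP 2.1.4.2. The event is outside every period of the row for TEAEs leading to death.
- Person-months in the TEAE overview are those within each analysis period, so the rates also describe a shorter window than the definition.
- SAP 2.5.3 ends TEAE status at the end of the recurrence episode when the first-dose date is missing, which is a third statement of the limit.

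**The case against.** The strongest counter-reading is that the residual epoch, being called a subdivision of the recurrence period, is capped at the end of that period. The missing-date rule in SAP 2.5.3 and the restriction in SAP 2.4.5.1 fit this, and no TEAE would then go untabulated. But with the visit on days 6 to 8, the 30-day limit would never operate in an episode on the planned schedule. It would matter only if drug stopped at least 23 days early or the visit was very late. Neither the epoch definition nor the two sections that rely on it mention a cap.

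Other points stand in part:

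- **Other tables.** SAP 2.4.5.1 also plans summaries of treatment-related serious events, hypersensitivity reactions and bleeding that may not be limited to TEAEs. Some late events probably appear there for the ITO population, but still grouped by ALX0681-C301 exposure. The SAP promises a separate description of posttreatment events, but defines no period for it, and under SAP 2.1.4 these events are not posttreatment.
- **Days, not events.** The documents give no event rate by day since last dose, so the percentages do not translate into a share of TEAEs. Counts differ only if an event starts in the gap.
- **Ascertainment.** After the recurrence follow-up visit, the next scheduled contact is a six-monthly visit. Non-serious events in the gap may be recalled less completely than those elicited at weekly visits, so a single pooled rate needs care.
- **Weight.** The analysis is descriptive, with no formal tests.

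**Conclusion.** The concern holds. For a treated episode on the planned schedule with no new recurrence, 22 to 24 of the 30 residual days (23 at the nominal visit) are inside the TEAE definition and outside every TEAE table period. On the assumed 5.9 PE days, that is about 35% of the TEAE window without extension and about 24% with the full extension. All of this assumes that the treatment period ends at the last dose.

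The events remain in the listings and the ITO tables. What is lost is their attribution to retreatment in the TEAE and treatment-related TEAE summaries. As written, those summaries can undercount and cannot overcount. By how much cannot be known from the documents. The SAP should be corrected, though the fault does not threaten the study's data.

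**What to change.** Leave the recurrence period as it is. The efficacy counts per recurrence period (SAP 2.4.4.1 and 2.4.4.2), and possibly the censoring of platelet response (SAP 2.1.3.2.1), depend on it. For safety only:

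1. Add to SAP 2.5.4, Table 1 and to the TEAE period list in SAP 2.4.5.1 a residual TEAE period. It runs from the day after the recurrence follow-up visit to last dose + 30 days, cut off at death, study termination or the start of a new episode. State that it is empty when the visit falls on or after last dose + 30 days.
2. Add an overall TEAE period from first dose to last dose + 30 days, with the same cut-offs and person-months to match. Keep the residual period on its own row, with a note on the sparser contact after the follow-up visit.
3. Amend the restriction in SAP 2.4.5.1 so that TEAE tables take every adverse event starting in the TEAE period.
4. Reword SAP 2.1.4 so that the epochs are no longer presented as subdivisions of the recurrence period.
5. Align the end limit in the missing first-dose rule of SAP 2.5.3.

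The cost is SAP wording, one more date derivation and two more safety table periods. No new data are needed, because Protocol 3.4.9.1 collects adverse events to the last visit. TEAE counts stay the same or rise, and efficacy outputs do not change.

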2.1.4.1 Adverse events variables

Adverse event observation period

- On-study adverse events are adverse events that developed or worsened or became serious during the on-study period
- Treatment-emergent adverse events are adverse events that developed or worsened or became serious during the treatment-emergent adverse event period

All adverse events (including serious adverse events (SAE)) will be coded to a lower-level term (LLT), preferred term (PT), high-level term (HLT), high-level group term (HLGT), and associated primary system organ class (SOC) using the version 22.0 of Medical Dictionary for Regulatory Activities (MedDRA).

2.1.4.2 Deaths

The deaths observation period is per the observation periods defined above.

- Death on-study: deaths occurring during the on-study observation period
- Death on-treatment: deaths occurring during the treatment-emergent adverse event period

2.1.4.3 Laboratory safety variables

Clinical laboratory data consists of blood analysis, including hematology, clinical chemistry, and urinalysis. Clinical laboratory values after conversion will be analyzed into standard international units and international units will be used in all listings and tables.

Blood samples for clinical laboratories will be taken according to the schedule of assessments. The laboratory parameters will be classified as follows:

- Hematology

Red blood cells and platelets and coagulation: hemoglobin [Hb], hematocrit [Hct], red blood cells [RBC], platelets)

White blood cells: white blood cells [WBC]

- Clinical chemistry

Metabolism: total cholesterol, total protein, C-reactive protein [CRP],

Renal function: creatinine

eGFR will be calculated using the CKD-EPI creatinine equation from Levey et al. (2009) (2):

$$eGFR = 141 * \min(SCr/\kappa, 1)^\alpha * \max(SCr / \kappa, 1)^{-1.209} * 0.993^{Age} * 1.018 \text{ [if female]} * 1.159 \text{ [if Black]}$$

Where:

eGFR (estimated glomerular filtration rate) = mL/min/1.73 m²

SCr (standardized serum creatinine) = mg/dL

κ = 0.7 if females or 0.9 if males

α = -0.329 if females or -0.411 if males

min = indicates the minimum of SCr/ κ or 1

max = indicates the maximum of SCr/ κ or 1

age = years

Liver function: alanine aminotransferase [ALT], aspartate aminotransferase [AST], lactate dehydrogenase [LDH]

Pregnancy test: Serum β -human chorionic gonadotropin (all female patients)

Urine samples will be collected as follows:

Urinalysis - quantitative analyses: albumin

- Disease related marker

Troponin, ADAMTS13 activity and time to sustained ADAMTS13 normalization $\geq 10\%$. will be analyzed.

Sustained ADAMTS13 activity $\geq 10\%$ is defined as two consecutive weekly visits during post-daily plasma exchange or follow-up visits at which ADAMTS13 activity is $\geq 10\%$. The first of these consecutive visits will be used to determine the event. The time to sustained ADAMTS13 activity $\geq 10\%$ is the time from the recurrence visit to the event. In case the event does not occur before the last visit in the recurrence episode, the patient is censored at the last visit.

Technical formulas are described in [Section 2.5.1](#).

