1.1.1. TREATMENT OF ACQUIRED TTP

Plasma exchange (PE) is the current standard of care for treatment of acquired TTP. PE replenishes ADAMTS13, partially normalizing vWF processing, and removes pathogenic autoantibodies. Daily exchanges are to continue for a minimum of 2 days after the platelet count has normalized [12]. Immunosuppression, most commonly in the form of corticosteroids is often started together with PE to reduce the production of autoantibodies. Despite standard of care treatment, an exacerbation occurs in approximately 30% of patients within 30 days of stopping PE [13]. Severe ADAMTS13 deficiency (<10%) has been identified as a potential biomarker of active underlying disease and an elevated risk of relapse in these patients [14, 15].

In spite of recent advances in understanding the disease, there are no approved pharmacologic therapies for acquired TTP. Caplacizumab represents a novel approach to treating the microthrombotic component of acquired TTP. Caplacizumab is being developed with the aim of preventing platelet consumption and formation of further microthrombi thereby reducing the duration of tissue ischemia and protecting the patient from the manifestations of the disease while the underlying process resolves. When used in conjunction with PE for initial and recurrent episodes of acquired TTP, its ability to prevent further microthrombus formation may translate into better long term outcomes for these patients.

[figure not shown]

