2.4.7 Analysis of disease-related markers

Troponin I and ADAMTS13 activity will be summarized using descriptive statistics for each time point on the recurrence and ITO populations. Line plot of the mean ADAMTS13 activity, including SE bars, will be provided.

Furthermore, for subjects experiencing a recurrence, time to sustained ADAMTS13 activity ≥ 10% will be summarized using KM estimates such as the median, 25% percentile and 75% percentile with associated 95% CIs, as well as the number of events and the number of censored observations. The KM estimates will also be presented graphically.

Troponin I and ADAMTS13 activity will also be listed.

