Study Visit	Recurrence Visit	Day 3 visit Treatment Day 3	Week 1 visit Post-daily PE Day 1 (1 day after last daily PE)		
Review of caplacizumab treatment criteria	X				
Pregnancy test ^a	X				
TTP recurrence information ^b	X		X		X
Study drug administration				>	
PE information			X		
Concomitant medication					>
Adverse events					>
Supine heart rate & blood pressure ^c	X	X	X	X ^d	X
Physical examination	X	X	X	X ^d	X
SF-36					X
Clinical laboratory analyses + urinalysis ^e	X	X	X	X	X
Organ damage markers: TnI ^f	X	X	X	X	X
ADAMTS13 activity ^f	X	X	X	X	X
Immunogenicity (ADA panel) ^{f,g}	X	X	X	X	X
PK ^f	X	X	X	X	X
PD parameters ^{f,h}	X	X	X	X	X

^a Pregnancy test (urine or blood) for female subjects of childbearing potential will be assessed per local laboratory.

^b TTP recurrence information includes presenting symptoms (assessed at recurrence visit), duration (assessed at the Week 1 visit) and outcome (assessed at the recurrence FU visit).

^c Heart rate and blood pressure to be assessed after 5 min in supine position.

^d To be assessed at the post-daily PE Day 29 only.

^e Clinical laboratory analyses include hematology (Hb, Hct, RBC, WBC, platelets); chemistry (AST, ALT, LDH, creatinine, protein, cholesterol and CRP). Urinalysis includes assessment of albumin. The results of assessment of platelet count and LDH levels performed as per standard of care (by a local laboratory) at any time during the recurrence period will be collected in the eCRF, if available.

- f* At the recurrence visit and the Treatment Day 3 visit, samples need to be collected prior to start of the PE treatment and/or study drug administration (whatever comes first). At all subsequent visits, blood samples need to be taken prior to study drug administration.
- g* In case of a severe and/or serious hypersensitivity reaction, an additional blood sample to characterize the reaction should be collected as soon as possible after the start of the event.
- h* PD parameters include RICO and vWF:Ag.

Table 6 Schedule of Assessments in Case of TTP Recurrence (in Case Treatment with Caplacizumab is not Initiated)

Study Period	Recurrence Period (no caplacizumab)	
	Recurrence Visit Recurrence Day 1	Recurrence FU visit 30 days after end of daily PE
TTP recurrence information ^a	X	X
PE information		X
Concomitant medication		→
Adverse events		→
Supine heart rate & blood pressure ^b	X	X
Physical examination	X	X
SF-36		X
Clinical laboratory analyses + urinalysis ^c	X	X
Organ damage markers: TnI ^d	X	X

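### The Kaplan-Meier curve for sustained ADAMTS13 activity of at least 10% includes episodes not treated with caplacizumab, whose visit schedule cannot produce the event

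*SAP*

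**What the plan says.** **Event.** SAP 2.1.4.3 defines sustained recovery as "two consecutive weekly visits during post-daily plasma exchange or follow-up visits at which ADAMTS13 activity is" at least 10%. On dating it says: "The first of these consecutive visits will be used to determine the event". The time "is the time from the recurrence visit to the event". The censoring rule is: "In case the event does not occur before the last visit in the recurrence episode, the patient is censored at the last visit".

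**Who is analysed.** SAP 2.4.7 takes everyone with a recurrence: "for subjects experiencing a recurrence, time to sustained ADAMTS13 activity" of at least 10% is to be summarised with Kaplan-Meier median and quartiles. It states no restriction to treated episodes and no grouping. The sections just before it do restrict: SAP 2.4.6.1 (PK) and 2.4.6.2 (RICO) are limited to patients treated with the study drug.

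**When ADAMTS13 is sampled.**
- Treated episodes (SAP Appendix A, Table 5): the Week 1 visit, labelled "Post-daily PE Day 1 (1 day after last daily PE"), then post-daily PE Days 8, 15, 22 and 29, then a follow-up visit 7 days after the end of treatment.
- Untreated episodes (SAP Appendix A, Table 6): the recurrence visit, sampled before the first PE, and one further visit, "Recurrence FU visit 30 days after end of daily PE".

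**Plasma exchange and the marker.** Protocol 1.1.1 states: "PE replenishes ADAMTS13, partially normalizing vWF processing, and removes pathogenic autoantibodies".

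**Unscheduled values.** SAP 2.5.5 lets unscheduled measurements count when time-to-event variables are derived.

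**The concern.** A Kaplan-Meier curve estimates when an event happens among people who could be seen to have it. An episode with one post-PE sample cannot supply two consecutive ones. Such an episode stays in the risk set and is then censored because of its visit schedule, whatever the patient's ADAMTS13 does. Mixed with treated episodes, it makes recovery look rarer and later than it was.

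The second issue is dating in treated episodes. The earliest visit that can date the event falls one day after donor plasma was last given daily, so the activity measured there may partly be the donor's. A second visit confirms the level but leaves the date at the first.

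ADAMTS13 below 10% is the documents' marker of unresolved disease (Protocol 1.2.4 and 1.2.5), and this curve is where the plan describes how quickly that marker resolves.

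**Working it through.** The plan states no event rate, sample size or expected median for this variable, so there is no figure to reproduce. The check counts qualifying visit pairs and then works through an illustration.

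**1. Qualifying pairs on scheduled visits (days after the last daily PE)**

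| Episode | Post-PE ADAMTS13 samples | Consecutive pairs | Earliest event date |
|---|---|---|---|
| Treated, no extension | 1, 8, 15, 22, 29, about 37 (30 + 7) | 5 | Day 1 |
| Untreated | 30 | 0 | none |

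The recurrence-visit sample in an untreated episode precedes the first PE, so it cannot be one of the pair. A later six-monthly visit does not help either, because the censoring rule closes the episode at its own last visit, which here is the only post-PE visit.

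**2. Effect of pooling**

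Without an extension, every treated event is dated Day 29 or earlier. Untreated episodes are censored at Day 30. With similar PE durations they are therefore at risk at every treated event time. If F(t) is the cumulative incidence in treated episodes and u the untreated share,

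pooled incidence = (1 − u) × F(t).

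Illustration. These are assumptions, apart from the PE duration, which is rounded from the 5.9-day mean in the caplacizumab arm of the Phase II study (Protocol 1.2.4):
- PE lasts 6 days.
- 60% or 80% of treated episodes recover.
- Recoveries are spread evenly over Days 8, 15, 22 and 29, which are days 14, 21, 28 and 35 from the recurrence visit.

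| u | Final incidence, F = 0.60 | Median | Final incidence, F = 0.80 | Median |
|---|---|---|---|---|
| 0% | 0.60 | day 35 | 0.80 | day 28 |
| 10% | 0.54 | day 35 | 0.72 | day 28 |
| 20% | 0.48 | not reached | 0.64 | day 35 |
| 30% | 0.42 | not reached | 0.56 | day 35 |
| 40% | 0.36 | not reached | 0.48 | not reached |

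For example, 0.60 × (1 − 0.20) = 0.48. Excluding untreated episodes reverses it: 0.48 / 0.80 = 0.60. Where treatment is extended, events can be dated after Day 30, when untreated episodes have already left the risk set, so the simple factor applies only to steps up to Day 30.

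**3. Dating to Day 1**

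The earliest pair is Day 1 with Day 8, dated Day 1. If Day 1 reflects donor enzyme and the patient's own activity is back by Day 8, the error is at most 8 − 1 = 7 days. Moving all Day 8 recoveries to Day 1 in the illustration shifts the first step from day 14 to day 7 and leaves every median unchanged.

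Tapering loosens that bound. Table 5, footnote f, asks for sampling before PE only at the recurrence and Day 3 visits; later samples need only precede study drug. Protocol 3.3.6 places the drug after PE on tapering days. A compliant weekly sample could thus follow a tapering exchange, and Day 8 could carry donor enzyme too. The documents give no residual donor activity, so the affected share could be anything from none to all.

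**The case against.** **The event is not impossible in untreated episodes.** A reader might infer a probability of exactly zero. The documents do not support that, because SAP 2.5.5 admits unscheduled measurements. The limit holds for scheduled visits. A second ADAMTS13 value looks unlikely, since Table 6 provides only for local platelet and LDH results to be added, but it is not excluded.

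**Pooling is not stated outright.** SAP 2.4.4 splits recurrence-period efficacy endpoints into treated and not treated, SAP 2.4.5 presents safety by treatment group, and SAP 2.5.4 has separate period tables. A reader might infer a single curve biased in both directions. That needs pooling, which is the plain reading of 2.4.7 but remains an ambiguity. If the split were applied, the treated curve would escape dilution, but the untreated curve would be flat. Restricting the analysis is right either way.

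**The two-visit rule already protects against donor plasma.** It does stop an isolated Day 1 value from creating an event. PE also removes autoantibodies, so a Day 1 value of at least 10% confirmed a week later may be genuine recovery. In the Phase II study, seven relapsing subjects stayed below 10% during treatment, so donor plasma does not necessarily mask active disease. These points stand, and they are why Day 1 should not simply be barred: doing so would misdate true early recoveries and subjects who were never below 10%.

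**Importance.** A reader might infer that the curve supports the treatment-extension rule. No section says so; Protocol 3.3.1 leaves that decision to the investigator, using weekly ADAMTS13 results and clinical signs. The variable is not among the protocol's main endpoints, no formal test is planned (SAP 2.4.4.8), and individual ADAMTS13 values are listed.

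**Conclusion.** The point holds for the analysis set. As written, SAP 2.4.7 admits episodes that cannot meet the definition in 2.1.4.3 on their scheduled visits. If pooled, they lower the cumulative incidence by about the untreated share; if shown separately, they give a flat and uninformative curve. The proportional reduction assumes similar PE durations, no extension and no extra unscheduled ADAMTS13 values. The untreated share is not in the documents, so the illustrated figures are not predictions.

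Early dating in treated episodes is a real but secondary concern. It affects only episodes at or above 10% on both Day 1 and Day 8 whose Day 1 value came from the donor. Without tapering it is at most about 7 days. With tapering no bound follows from the documents.

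This is a minor point in a descriptive study.

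**What to change.** 1. In SAP 2.4.7, limit this Kaplan-Meier analysis to episodes treated with caplacizumab, using the same restriction as for PK and RICO. For untreated episodes, summarise the single follow-up ADAMTS13 value descriptively, for example as the number and percentage at or above 10%.
2. Keep the definition in SAP 2.1.4.3 as the main analysis. Add one sensitivity analysis in which post-daily PE Day 8 is the earliest possible event date and samples taken during PE tapering do not qualify. State in the SAP how the tapering period is identified from the recorded PE dates.

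The cost is SAP wording, slightly more analysis work and a smaller Kaplan-Meier population. No new data are needed. The sensitivity analysis will date some genuine early recoveries late, which is why it should stand beside the main analysis and not replace it.
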